2.2 Secondary estimands

The clinical questions of interest are:

- What is the effect of secukinumab 150 mg s.c. versus placebo on the composite endpoint ACR50 response at week 16 and the completion of 16 week-treatment in Chinese patients with active PsA?
- What is the effect of secukinumab 150 mg s.c. versus placebo on change from BSL in DAS28-CRP at week 16 in Chinese patients with active PsA had patients completed 16 week-treatment?
- What is the effect of secukinumab 150 mg s.c. versus placebo on change from BSL in PASDAS at week 16 in Chinese patients with active PsA had patients completed 16 week-treatment
- What is the effect of secukinumab 150 mg s.c. versus placebo on change from BSL in SF-36 PCS at week 16 in Chinese patients with active PsA had patients completed 16 weektreatment?
- What is the effect of secukinumab 150 mg s.c. versus placebo on change from BSL in HAQ-DI at week 16 in Chinese patients with active PsA had patients completed 16 week-treatment?

The justification for targeting the treatment effect is that we wish to estimate the effect of the study drug for the full duration when administered without dose changes.

The estimand definition of all secondary objectives related to response (e.g., ACR50, etc.) will have the same attributes as that for the primary estimand, except for the variable of interest.

Estimand definition for the secondary continuous variables (e.g., $HAQ-DI^{\odot}$, etc.) is the following:

- a. Population: defined through appropriate inclusion/exclusion criteria to reflect the targeted PsA population
- b. Variable: change from BSL in the variable of interest
- c. Intercurrent event: discontinuation from treatment or study prior to Week 16
- d. Population-level summary: difference in variable means between secukinumab and placebo groups

3 Study design

This bridging study uses a randomized, double-blind, placebo-controlled, parallel-group design. A screening period running up to 10 weeks before randomization will be used to assess participant eligibility followed by 52 weeks of treatment.

At BSL, approximately 40 Chinese participants whose eligibility is confirmed will be randomized to one of two treatment groups in 1:1 ratio:

• Group 1 - secukinumab 150mg s.c. :

Secukinumab 150 mg (1.0 mL PFS of 150 mg dose) administered at BSL, Weeks 1, 2, and 3 followed by dosing every four weeks starting at Week 4.

• Group 2 - placebo s.c.

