¹ If subject's washout period is \leq 4 weeks, two screening visits can be performed on the same day.

² These assessments are also to be conducted for patients who discontinue from the treatment-Treatment Discontinuation (TD): Patients who prematurely discontinues during Treatment Period 1 has to return for assessments associated with End of TP1 visit (4 weeks after the last study treatment) and End of study visit (12 weeks after the last administration of the study treatment). Patients who prematurely discontinues during Treatment Period 2 has to return and complete assessments associated with End of TP2 visit (4 weeks after the last administration of the study treatment) and End of study visit (12 weeks after the last administration of the study treatment) and End of study visit (12 weeks after the last administration of the study treatment).

³ To determine the duration of the washout period, and if the second screening visit will be performed (see Section 8.1).

⁴ assessment to be recorded on source documentation only

⁵ Either a QuantiFERON TB-Gold test or a PPD skin test must be performed at Screening. A QuantiFERON TB-Gold test is to be performed at the second screening visit. The PPD skin test can be performed at any time during the screening period but it has to be read within 72 hrs and before randomization.

⁶ Sample will be analyzed locally

⁷ If patients do not have a chest X-ray available within 3 months of screening, an X-ray is to be performed after it is certain the subject meets inclusion/exclusion criteria in order to minimize unnecessary exposure to X-ray radiation. The x-ray might be replaced by an MRI assessment.

⁸ Patients will be re-randomized at Week 16.

⁹ Recommended to perform urine pregnancy test at designated visits in local lab, if not feasible alternatively the serum pregnancy test should be performed. A positive urine test requires immediate interruption of study drug and needs to be confirmed with a serum Beta human chorionic gonadotropin (β-hCG test) (serum pregnancy test). If positive, the participant must be discontinued from the study treatment.

¹⁰ AEs/SAEs occurring after the participant has signed the informed consent must be captured on the appropriate eCRF page.

¹¹ Since the results of this test may unblind study personnel, results from the central lab will be provided for SCR and BSL only. The hsCRP results from samples collected during the treatment period will be revealed following database lock only

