The appropriate personnel from the site and Novartis will assess whether study treatment should be discontinued for any participant whose treatment code has been broken inadvertently for any reason.

Participants who prematurely discontinued from study treatment during Treatment Period 1 had to return for assessments associated with End of TP1 visit (4 weeks after the last study treatment) and the End of study visit (12 weeks after the last study treatment). Participants who prematurely discontinued during Treatment Period 2 had to return and complete assessments associated with End of TP2 visit (4 weeks after the last study treatment) and End of study visit (12 weeks after the last study treatment) and End of study visit (12 weeks after the last study treatment) and End of study visit (12 weeks after the last study treatment) and End of study visit (12 weeks after the last study treatment) and End of study visit (12 weeks after the last study treatment) and End of study visit (12 weeks after the last study treatment) and End of study visit (12 weeks after the last study treatment) and End of study visit (12 weeks after the last study treatment) and End of study visit (12 weeks after the last study treatment) and End of study visit (12 weeks after the last study treatment) and End of study visit (12 weeks after the last study treatment) and End of study visit (12 weeks after the last study treatment) and End of study visit (12 weeks after the last study treatment).

- Participants unwilling to continue attending further study visits after prematurely discontinuing the study treatment should return for the end of study (EOS) visit 12 weeks after the last administration of the study treatment.
- Participants willing to continue attending study visit should continue attending all subsequent scheduled site visits for clinical and safety study assessments, except study treatment administration.
- Participants initially continue attending site visits after premature study treatment discontinuation may decide to discontinue study at any time. For those participants, the EOS visit will be performed at time of study discontinuation. Note: the EOS visit must always be completed at least 12 weeks after the last study treatment administration.

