12.4.3 Handling of missing values/censoring/discontinuations

Missing data for ACR20 response and other binary efficacy variables (e.g., ACR50, etc.) for data up to Week 16 will be handled as follows:

- 1. participants who discontinue from treatment or study for any reason will be considered as non-responders from the time of discontinuation through Week 16
- 2. participants who do not have the required data to compute ACR responses (i.e., tender and swollen joint counts and at least three of the five ACR core set variables) at BSL and at the specific timepoint will be classified as non-responders at the specific timepoint.

participants who are unblinded prior to the scheduled time point will be considered nonresponders from the time of unblinding up to Week 16. The primary analysis will use the nonresponder imputation.

Continuous variables (e.g., ACR components, etc.) will be analyzed using a mixed-effects model repeated measures (MMRM) which is valid under the missing at random (MAR) assumption. As such, single-point imputation of missing data will not be performed (e.g., LOCF). For analyses of these parameters, if all post-BSL values are missing then these missing values will not be imputed and this participant will be removed from the analysis of the corresponding variable, i.e., it might be that the number of participants providing data to an analysis is smaller than the number of participants in the FAS.

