2.6 Analysis of the secondary objectives

2.6.1 Secondary endpoints

The secondary efficacy variables are described below. Secondary efficacy variables were analyzed using the FAS population. Handling of missing data for secondary variables were the same as for the primary variable.

- ACR50 response rate at Week 16

- Change from baseline in DAS28-CRP at Week16
- Change from baseline in PASDAS at Week 16
- Change from baseline in SF36-PCS at Week 16
- Change from baseline in HAQ-DI[©] at Week 16

The clinical questions of interest are:

- What is the effect of secukinumab 150 mg s.c. versus placebo on the composite endpoint ACR50 response at week 16 and the completion of 16 week-treatment in Chinese patients with active PsA?
- What is the effect of secukinumab 150 mg s.c. versus placebo on change from BSL in DAS28-CRP at week 16 in Chinese patients with active PsA had patients completed 16 week-treatment?
- What is the effect of secukinumab 150 mg s.c. versus placebo on change from BSL in PASDAS at week 16 in Chinese patients with active PsA had patients completed 16 week-treatment?
- What is the effect of secukinumab 150 mg s.c. versus placebo on change from BSL in SF-36 PCS at week 16 in Chinese patients with active PsA had patients completed 16 week-treatment?
- What is the effect of secukinumab 150 mg s.c. versus placebo on change from BSL in HAQ-DI at week 16 in Chinese patients with active PsA had patients completed 16 week-treatment?

The justification for targeting the treatment effect is that we wish to estimate the effect of the study drug for the full duration when administered without dose changes.

The estimand definition of all secondary objectives related to response (e.g., ACR50, etc.) will have the same attributes as that for the primary estimand, except for the variable of interest.

Estimand definition for the secondary continuous variables (e.g., HAQ-DI[©], etc.) is the following:

- a. Population: defined through appropriate inclusion/exclusion criteria to reflect the targeted PsA population
- b. Variable: change from baseline in the variable of interest
- c. Treatment of interest: Secukinumab 150 mg s.c. and Placebo
- d. Intercurrent event: discontinuation from treatment or study prior to Week 16
- e. Population-level summary: difference in variable means between secukinumab and placebo groups

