Group 9: ANA, anti-dsDNA

The following rules are used to determine the window for an applicable visit post baseline
“Lower limit” = “upper limit of prior applicable visit” + 1. “Upper limit” = “target day of current visit” + integer part of (“target day of next applicable visit” - “target day of current visit”)/2. Lower limit of the first applicable visit is always Day 2. Day 1 is the date of the first dose of randomized study treatment.

The mapping described above applies to all visits (not just scheduled visits). Repeat and/or unscheduled visits (which will be numbered in the database according to new NCDS standards) will be mapped for analysis purposes in the same way as scheduled visits. This leaves the possibility, then, for multiple measurements within an analysis window. If more than one assessment falls into the interval, the rules defined in Section 5.1.2 below are applied.

Re-randomization will be performed at the end of treatment period 1, assessment from treatment period 2 will not be considered for treatment period 1, e.g., if a Week 20 (scheduled visit) measurement would fall into the Week 16 visit window, this measurement would not be analyzed as treatment period 1 value. Of note, for subjects who discontinue in treatment period 1, i.e., not moving into treatment period 2, measurements taken in follow-up period would still be considered for treatment period 1.

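### As written, the Week 16 MMRM for the continuous secondary endpoints keeps values recorded after treatment stopped, although the stated question is hypothetical

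*SAP*

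**What the plan says.** **The question.** Protocol 2.2 asks, for each of DAS28-CRP, PASDAS, SF-36 PCS and HAQ-DI, for the effect on change from baseline "at week 16 in Chinese patients with active PsA had patients completed 16 week-treatment". SAP 2.6.1 repeats this, for example for "HAQ-DI at week 16 in Chinese patients with active PsA had patients completed 16 week-treatment". The attributes of the continuous estimand list the event ("Intercurrent event: discontinuation from treatment or study prior to Week 16") and stop there. The primary estimand, by contrast, absorbs the same event into its composite variable.

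**Data after stopping.** Under Protocol 9.1.1, participants who stop treatment and are willing "should continue attending all subsequent scheduled site visits for clinical and safety study assessments", without dosing. Table 8-1 schedules joint counts, VAS scales, HAQ-DI and hsCRP at the visits up to Week 16, and SF-36 at Weeks 4, 8, 12 and 16.

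**Where the data go.** SAP 5.1.1 maps scheduled and unscheduled visits alike to analysis windows. It bars Period 2 measurements from Period 1 but says of people who stop in Period 1 that "measurements taken in follow-up period would still be considered for treatment period 1".

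**The model.** Protocol 12.4.3 analyses continuous variables with a "mixed-effects model repeated measures (MMRM) which is valid under the missing at random (MAR) assumption". A participant drops out of the analysis only if every post-baseline value is missing. Section 12.5.1 gives the MMRM for DAS28-CRP, PASDAS and HAQ-DI. For SF-36 PCS, the visible text of 12.5.3 gives only summaries of observed data.

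**Scope.** The supplied SAP covers the final database lock. Its sections 2.5.2, 2.5.3, 2.6.2 and 2.6.3 refer the Week 16 methods to a separate SAP for the primary endpoint analysis.

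**The concern.** A hypothetical question about completing treatment is not answered by outcomes measured after treatment has stopped. The usual implementation treats those outcomes as missing and lets the MMRM predict them under MAR. MAR deals with absent values; it does not turn an observed off-drug value into an on-treatment one. If the values stay in, the MMRM estimates a treatment-policy effect under a hypothetical label.

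The trial expressly pursues estimation rather than testing (Protocol 12.8.1), so what is being estimated should be unambiguous. If benefit fades after stopping, the reported difference is smaller than the one asked for. Four of the five secondary efficacy endpoints carry the hypothetical question.

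**Working it through.** **1. The plan's own figure.** The only design figure is the probability of success in Protocol Table 12-1 (SAP Table 3-1). With X1 ~ Bin(20, 0.514) and X2 ~ Bin(20, 0.231), exact enumeration of P(X1/20 − X2/20 > c) gives 0.860 for c = 0.1415 and 0.960 for c = 0, as stated. It concerns ACR20 and does not change. The documents give no discontinuation rate and no figure for loss of effect after stopping.

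**2. Where values after stopping land.** SAP target day = 1 + 7 × week, so Week 16 is Day 113. The Week 16 window is Day 100-127 for ACR components and hsCRP, and Day 100-141 for SF-36. Participants who stop in Period 1 "return for assessments associated with End of TP1 visit (4 weeks after the last study treatment"), per Protocol Table 8-1, footnote 2, and Section 9.1.1. This is the TD visit.

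| Last dose | Day | TD visit (day + 28) | Weeks from last dose to Day 113 |
|---|---|---|---|
| Week 4 | 29 | 57 (Week 8 window) | (113 − 29)/7 = 12 |
| Week 8 | 57 | 85 (Week 12 window) | (113 − 57)/7 = 8 |
| Week 12 | 85 | 113 (Week 16 window) | (113 − 85)/7 = 4 |

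Someone last dosed at Week 4 or Week 8 who keeps attending therefore supplies a Week 16 value 12 or 8 weeks after the last dose. After a Week 12 dose, the Week 16 value is one dosing interval old and raises no issue.

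**3. Is F60 a route?** The end-of-study visit falls 84 days after the last dose; after a Week 4 dose that is Day 29 + 84 = Day 113, inside the Week 16 window. But Table 8-1 schedules no joint counts, VAS, HAQ-DI, hsCRP, ESR or SF-36 at that visit. The affected efficacy data come from continued scheduled visits.

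**4. Is there a rule that removes them?** Protocol 12.4.3 makes binary endpoints non-response from discontinuation to Week 16. It has no counterpart for continuous endpoints. Elsewhere the protocol declares data missing after consent withdrawal (9.1.2) and for assessments not feasible in a pandemic (16.9). Neither covers stopping treatment.

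**5. Size.** Let q be the share of the secukinumab arm that stops and keeps attending, and r the share of effect retained at Week 16. Assume that stopping placebo changes nothing. The all-data difference as a share of the on-treatment difference is (1 − q) + q × r.

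| q | r = 0 | r = 0.5 |
|---|---|---|
| 5% (1 of 20) | 0.95 | 0.975 |
| 10% (2 of 20) | 0.90 | 0.95 |
| 15% (3 of 20) | 0.85 | 0.925 |
| 20% (4 of 20) | 0.80 | 0.90 |

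**6. Model check.** A large-sample normal-likelihood simulation (unstructured covariance; visits at Weeks 4, 8, 12 and 16; SD 1.2, correlation 0.6; random stopping after Week 4 or 8) was run for q = 5%, 10% and 20%. With all values kept it gave 0.958, 0.898 and 0.801 at r = 0, and 0.981, 0.949 and 0.899 at r = 0.5. With values after stopping removed it gave 0.996 to 1.011. Stopping was random by construction, so this shows which question each data set answers, not that MAR holds in the trial.

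**The case against.** The strongest reply is that the governing Week 16 plan is not in hand. It may already exclude values after discontinuation. The supplied SAP specifies no MMRM, and SAP 2.10 says that the Week 16 analysis is done and was used for submission. This stands. It makes the point conditional and means that editing the supplied SAP alone would not change the Week 16 estimate. It does not clear the protocol, which defines the question and the model and has no such rule.

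Four stronger readings are tempting, and the documents do not support them:

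- **Follow-up efficacy data are pulled into Week 16.** The SAP 5.1.1 sentence suggests this, but F60 has no scheduled efficacy measures (step 3).
- **Placebo participants rescued with a biologic add Week 16 values on that biologic, doubling the shrinkage.** Protocol Section 3 and Section 6.2.3 send them to follow-up, and footnote 1 of Table 6-2 requires study discontinuation. The Table 6-2 action column and Section 9.1.1 could be read as allowing continued visits. The text is inconsistent, and no larger range can rest on it.
- **All four endpoints use the MMRM.** It is visible for three. Only the general sentence in 12.4.3 could extend it to SF-36 PCS, and text nearby may be redacted.
- **The reported Week 16 estimates are biased.** That would need the unsupplied SAP and actual early stoppers who kept attending.

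It is also fair that only willing participants attend after stopping. For the rest, values are missing and the MAR model fits the stated question.

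**Conclusion.** The mismatch is real on the supplied text: a hypothetical question, an unstated strategy, collection of off-treatment values, mapping that admits them, and a model with no rule to exclude them. It is more than missing detail, because following the written rules answers a different question.

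The size is unknown. The 5-15% range assumes that 1 to 3 of 20 secukinumab participants stop early enough, all keep attending, and all effect is gone by Week 16. With half the effect retained it is 2.5-7.5% (5% × 0.5 to 15% × 0.5), and with no early stoppers it is zero. The conclusion depends on the Week 16 SAP not already holding the rule. The point should be fixed, but it is confined to the continuous secondary endpoints: ACR20 and ACR50 are protected by non-responder imputation.

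**What to change.** 1. Check whether the Week 16 SAP already excludes continuous efficacy values after treatment discontinuation. If so, cite that rule in Protocol 2.2 and 12.4.3 and in the supplied SAP.
2. If not, state the hypothetical strategy in Protocol 2.2 and 12.4.3 and in the Week 16 SAP. Set continuous efficacy values after discontinuation to missing before the MMRM, keeping those up to and including the TD visit 4 weeks after the last dose. Make the SAP 5.1.1 mapping consistent with this.
3. Rerun the Week 16 MMRM with this flag, labelled as an additional analysis. Report the analysis of all observed values as a treatment-policy sensitivity analysis, with the number of participants per arm whose values differ between the two.
4. Reconcile the protocol passages on attendance after use of a prohibited biologic (Section 3, Table 6-2 and its footnote 1, 6.2.3 and 9.1.1), so that it is clear whose later values can exist.

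The cost is wording, one data flag and possibly a supplementary rerun of a completed analysis. A few observed values leave the main secondary models but remain in the sensitivity analysis. No sample-size figure changes.

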5.1.2 Multiple assessments within visit windows

When there are multiple assessments in a particular visit window, the following rules are applied to select one value “representing” the subject in summary statistics in a visit window (See Table 5-2).

For baseline assessment definition, please see Section 2.1.1.3. For post-baseline visit windows, the following applies (unless otherwise specified):

- for *quantitative variables*, the *closest* to the actual visit is chosen (if two assessments have the same distance, then the earlier one will be chosen);
- for *qualitative variables*, the *worst* record is selected. It is noted that in the analyses performed, *worst* case is always well defined (e.g., for urine protein values “+” and “++”, the worst case is defined as “++”),
- in case qualitative variables are based on quantitative variables, [REDACTED], the visit will be assigned to the quantitative variable, and this visit will be used for the derived qualitative variable.

Table 5-2 Rules for selecting values for analysis within a given visit window

Timing of measurement	Type of data	Rule
Baseline	All data	
The last non-missing measurement made prior to or on the date of administration of the first dose of study treatment (the reference start date / Day 1). If a patient did not receive any dose of study treatment, then the randomization date will be used. Only date part is considered if just one assessment on Day 1.
 
If there are multiple assessments on Day 1, following rules will apply:
 
a. If assessment time exists, * select the last available measurement prior to reference start date/time considering time; * if no measurement prior to reference start date/time considering time, select the earliest measurement post reference start date/time considering time.

		
b. If assessment time does not exist, select the available measurement from the lowest CRF visit number.
 
For X-ray, a baseline value is the last measurement prior to dosing if available. Otherwise, take the first value within 30 days post dosing.
 
For MRI, a baseline value is the last measurement prior to dosing if available. Otherwise, take the first value within 7 days post dosing.

Post-baseline efficacy	All data	
For visits without switch of treatment in the window, the measurement closest to the target will be used. In the event two measurements are taken equally apart (e.g., 1 before target date and 1 after) the first one will be used.
 
For visits during which the patient switches from placebo to AIN the following will be done based on whether or not the patient met the rescue criteria:
 
a. if the analysis visit window is <= week 16, then
 
- if available, the closest measurement to the target date which is ON or BEFORE the switch date will be used (i.e., the closest measurement to target which is on placebo)- if there are no data on or before the switch then the closest measurement to the target date after the switch will be used 
b. if the analysis visit window is > week 16, then
 
- if available, the closest measurement to the target date which is AFTER the switch date will be used (i.e., the closest measurement to target which is on AIN)- if there are no data AFTER the switch then the closest measurement to the target date before the switch will be used 
Cases where the same parameter is recorded more than once on the same date will be handled as follows:
 
* if time of completion exists the earliest measurement will be used;* if time does not exist the measurement from the lowest CRF visit number will be used
Post-baseline safety	Summary visit information (e.g., lab, ECG, etc.)	
For visits without switch of treatment in the window, the measurement closest to the target will be used. In the event two measurements are taken equally apart (e.g., 1 before target date and 1 after) the first one will be used.
 
For visits during which the patient switches from placebo to AIN the following will be done based on whether or not the patient met the rescue criteria:
 
a. if the analysis visit window is <= week 16, then
 
- if available, the closest measurement to the target date which is ON or BEFORE the switch date will be used (i.e., the closest measurement to target which is on placebo)- if there are no data on or before the switch then the closest measurement to the target date after the switch will be used 
b. if the analysis visit window is > week 16, then
 
- if available, the closest measurement to the target date which is AFTER the switch date will be used (i.e., the closest measurement to target which is on AIN)- if there are no data AFTER the switch then the closest measurement to the target date before the switch will be used 
Cases where the same parameter is recorded more than once on the same date will be handled as follows:

		* if time of completion exists the earliest measurement will be used; * if time does not exist the measurement from the lowest CRF visit number will be used
Post-baseline safety	Notable abnormalities (e.g. lab)	The most extreme measurement in the window will be used. Note this means a patient can have a notably high and notably low measurement within a window.

